For the first part of the study, where full AUC analysis will be performed to verify the dose, we anticipate initially enrolling 12 patients to achieve 12 dose verifications. Any patients who do not achieve a complete PK data profile (i.e. due to suboptimal dose or incomplete course of study drug) will be replaced to achieve 12 dose verifications. The total number of patients will still remain 65 (Phase I and Phase II). The age of enrollment for these patients will be limited to 2-12 years old. This age restriction has been imposed because adult dosing for maraviroc in the stem cell transplant setting has already been established and it is likely that teenagers metabolize the drug similar to adults. The second part of the study, where full AUC analysis will not be conducted, will enroll the remaining patients between the ages 2-40 years.

We will enroll eligible patients and maraviroc will be administered as per study rules. Area under the concentration-time curve (AUC) determination will be performed on days 0 +/- 3 days and 10 +/- 3 days to account for weekends, national holidays or clinical deterioration not allowing for scheduled blood draws on the specified days. PK analysis will be performed after the first 3 patients. As per our study design graph, this is not an "interim" analysis, but an analysis to verify PK target attainment which then will drive either further observation or dose escalation. See Figure 1.

[figure not shown]

Figure 1. Study design

Pharmacokinetic measurement and analysis-

Blood for PK will be collected on day 0 +/- 3 days and Day 10 +/- 3 days. Complete PK profile (full AUC) will be performed on these days (see time points below). Evaluation of maraviroc trough levels will also be done routinely on all patients on study on days 0,7,14 and 21 in order to collect additional PK data, verify compliance and allow for additional dose corrections if necessary.

Target AUC/12 hours= $\geq 100\text{ng/mL}$ (based on HIV data)

PK processing will be performed at University of North Carolina's Clinical Pharmacology and Analytical Chemistry Laboratory using mass spectrometer with HPLC separation.

Plasma Maraviroc concentration data will be analyzed by compartmental and non-compartmental analysis with the help of [name], Director of Pediatric Pharmacology Research Unit (PPRU) at CCHMC, and parameter estimates generated will include clearance, half-lives, and volume of distribution along with area under the curve (AUC).

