While data on Maraviroc blood levels are available from other studies, our patients are different from those previously studied, and these first cases will be of great value in determining the levels of drug we can achieve in this population

The time points of obtaining drug levels will be as follows:

- Hour 0- Pre maraviroc administration
- Hour 1 \pm 10 minutes - After maraviroc administration
- Hour 2 \pm 10 minutes- After maraviroc administration
- Hour 4 \pm 10 minutes- After maraviroc administration
- Hour 6 \pm 10 minutes- After Maraviroc administration
- Hour 8 \pm 10 minutes- After maraviroc administration
- Hour 12 \pm 20 minutes- After Maraviroc administration

Plasma concentration-time data will be explored graphically and the AUC will be estimated by non-compartmental analysis with the software package WinNonlin (Version 6.2, Pharsight Corporation, Palo Alto, CA). Full maraviroc PK profile and trough concentration data will be analyzed using a PK model-based Bayesian approach (MW/Pharm, MediWare, Groningen, the Netherlands).

Pharmacodynamic analysis will be performed in the laboratory using standard techniques.

Pharmacodynamic assessments will occur on days 0 +/-3 days and one time on day 14 +/- 3 days after stem cell infusion. Results will be available in a timely fashion to correlate with pharmacokinetic test results.

Dose escalation criteria-

Dose escalation will take place if all the requirements listed below are met:

1. The AUC/12 hours of the initial 2/3 patients is below 100 ng/ml

2. No more than 0 of 3 or 1/6 patients on the first dose level experience a dose limiting toxicity by day 30, defined as either-
 - a. Non-engraftment by day 30. Engraftment is defined as the first of three consecutive measurements of ANC>500/mcL over 3 or more days.
 - b. Grade 4 liver abnormalities, unless clearly related to stem cell transplant and not to the study drug, including but not limited to grade 4-5 liver toxicity due to hepatic veno-occlusive disease, grade 4-5 organ toxicities related to expected infections following stem cell transplant and their sequelae, or grade 4-5 toxicities related to graft versus host disease.

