 - c. Other grade 4-5 toxicity , unless clearly related to stem cell transplant and not to study drug, including but not limited to veno-occlusive disease of the liver, acute graft versus host disease, autoimmune cytopenias, infectious complications due to stem cell transplant, or organ toxicities due to conditioning regimens.

BSA	Original Dose	Dose escalation	Value increment/dose
<0.22	40 mg bid	50 mg bid	+ 10 mg
0.2-0.43	100 mg bid	120mg bid	+ 20 mg
0.44-0.72	200 mg bid	250 mg bid	+ 50 mg
0.73-1.19	300 mg bid	350 mg bid	+ 50 mg
1.20-1.30	300 mg bid	350 mg bid	+ 50 mg
1.31-1.73	300mg bid	350 mg bid	+ 50 mg
>1.73	300 mg bid	350 mg bid	+ 50 mg

Table 4. Table showing doses and increments for dose escalation of Maraviroc.

Stopping Rules

1. If the incidence of Grade 2-4 acute GI or Liver (visceral) graft versus host disease is greater than 50% in the first 20 subjects by day +100, the study will be stopped. Enrollment will not stop while the analysis is being conducted.

2. If 3 out of 6 subjects experience DLT by day +30 as defined above at the initial dose in the first phase (AUC analysis) of the study, the study will be stopped. Enrollment will not be suspended while the analysis is being conducted.
3. The study will be halted for any grade 4 liver toxicity occurring within 30 days of study drug administration and without clear attributable alternative cause. Enrollment will be suspended while an analysis of the toxicity is being conducted. Enrollment will only restart with approval of the Medical Monitor, IRB and FDA. (Of note: any grade 3 liver toxicity (ALT > 5xULN or Total Bilirubin > 3xULN), regardless of cause, will lead to permanent discontinuation of Maraviroc for that specific patient, but enrollment will continue.)

Primary study end points

1. Feasibility
2. GVHD incidence by day +100 (all grades)
3. pK target >100ng/ml

Secondary Study end points

1. Overall survival by day +100
2. Graft failure by day + 100
3. Primary disease relapse by day +100
4. Incidence of toxicities either due to drug or transplant
5. Infectious complications which include asymptomatic viremias for EBV, Adenovirus, CMV, and/or viral disease, bacterial and fungal infections as documented by blood cultures.
6. Time to neutrophil and platelet engraftment

GVHD will be graded according to IBMTR criteria as shown in table 5 [33]-

	Stage 0	Stage 1	Stage 2	Stage 3	Stage 4

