Study calendar for blood draws for patients undergoing formal AUC analysis-

Days	AUC	Trough drug level	Pharmacodynamic assessment
Pretransplant			x
Day 0	X (± 3 days)		X (± 3 days)
Day 7		x (± 2 days)	
Day 10	X (± 3 days)		
Day 14		x (± 3 days)	X (± 3 days)
Day 21		x (± 3 days)	

Table 6. Study calendar for blood draws for patients undergoing formal AUC analysis

For patients enrolled after maraviroc dose has been verified, the schedule for lab draws is shown on Table 7.

Days	Trough drug level	Pharmacodynamic assessment
Pretransplant		x
Day 0	x (± 3 days)	X (± 3 days)
Day 7	x (± 2 days)	
Day 14	x (± 3 days)	X (± 3 days)
Day 21	x (± 3 days)	

Table 7- Study calendar for blood draws for patients on second phase of study (after PK study complete and dose verified)

Volume of Blood Draws-

For pharmacokinetic analysis, we will need approximately 3 ml of blood, to be collected in an EDTA tube. Real time data results will be available to allow for dosing changes to

be made after the first 3 patients. For pharmacodynamics analysis, we will need 2 ml blood in a sodium heparin tube.

Discontinuation of therapy-

Since most patients experience severe toxicities while undergoing an allogeneic SCT, it will be the investigator's responsibility to determine whether certain adverse events are related to the study drug or not based on previous studies using the agent and the current labeling. Common Terminology Criteria for Adverse Events (CTCAE) version 4.0 will be used to report toxicities.

The following events will mandate stopping Maraviroc for a specific patient;

- Grade 3 liver toxicity (ALT > 5xULN or Total Bilirubin > 3xULN) regardless of cause

Maraviroc will not be restarted in these cases.

The following events will mandate holding Maraviroc therapy on a specific patient:

1. Grade 3 or higher toxicity (exclusive of liver toxicity, see section above), not attributable to underlying disease.
2. Infection, which requires treatment with a strong CYP450 inducer or inhibitor (predicted to adversely interact with Maraviroc) such as rifampin.
3. Drop in renal function to creatinine clearance <40 ml/min as measured by GFR or cystatin C.

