The drug can be restarted at the same dose after full recovery from the AEs. Maraviroc will be discontinued if the AE recurs after re-challenge. Any grade 3 liver toxicity (ALT > 5xULN or Total Bilirubin > 3xULN) regardless of cause will lead to permanent discontinuation of Maraviroc for that patient. The study will be halted for any grade 4 liver toxicity occurring within 30 days of study drug administration without clear attributable alternative cause (see stopping rules for details). Re-challenge is not permissible in the event of Grade 3 or higher liver toxicity (ALT > 5xULN or Total Bilirubin > 3xULN) regardless of cause. Any grade 1 or 2 toxicities related to study drug will not require study drug to be held.

Early termination of study drug-

Treatment will continue unless one of the following criteria applies:

1. A dose limiting toxicity (DLT) occurs. A DLT is defined as either-
 - a.) Non-engraftment by day 30, if assessed by the investigator to be related to the study drug. Engraftment is defined as the first of three consecutive measurements of ANC>500/mcL over 3 or more days.
 - b.) Grade 4 liver abnormalities, once other causes for liver toxicity have been ruled out.
 - c.) Other grade 4-5 toxicity determined by the investigator to be related with high probability to the study drug.
2. Any grade 3 or higher liver toxicity (ALT> 5xULN or Total Bilirubin > 3xULN) regardless of cause:
 - a. Any grade 3 liver toxicity (as defined above) will lead to permanent discontinuation of Maraviroc for that patient.
 - b. The study will be halted for any grade 4 liver toxicity occurring within 30 days of study drug administration without clear attributable alternative cause. (See stopping rules for specific details.)
3. Patient decides to withdraw from the study due to inability to take the drug.
4. Poor compliance to drug (missing either 6 consecutive doses (3 days) or 12 intermittent doses in the entire administration period (< 80% compliance)).

Patients removed from study for unacceptable adverse events will be followed until the adverse event resolves or stabilizes.

Toxicity Monitoring-

Maraviroc is generally well tolerated in children as noted in the phase 1 congenital HIV trial. However, a black box warning for hepatotoxicity exists. Therefore, liver function tests will be monitored on patients while on maraviroc every 48 hours until day+30 (+ 7 days).

General concomitant medication and supportive care guidelines

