Maraviroc is not known to significantly affect any metabolic pathway. However, inhibitors and inducers of the cytochrome P450 metabolic pathway affect its drug level. Generally, patients in this trial will receive prophylactic antifungals as directed by their attending physician, which may include either micafungin or ambisome. Other concomitant medications are allowed except for strong inducers or inhibitors of the cytochrome P450, such as voriconazole, phenytoin, carbamazepine and rifampin. (See table 2).

Should there be emesis within 30 minutes of taking maraviroc, the drug should be re – administered. However, any emesis after 30 minutes of taking maraviroc will not require the drug to be readministered.

Risk to unborn fetus-

It is recommended that patients on study utilize appropriate methods of contraception to prevent getting pregnant or fathering a child as the effects of maraviroc on the unborn fetus is unknown. All female patients routinely undergo a pregnancy test as part of pre bone marrow transplant evaluation and only proceed with transplant when it is confirmed that they are not pregnant. Therefore we will not repeat this test prior to starting maraviroc.

Risk associated with blood draws-

This study will require research blood to be drawn as specified time points as shown in the study calendar. This blood will be drawn from a central line whenever possible and will be combined with routine clinical blood draws whenever possible and will not exceed maximum allowed blood volume for that patient per day per standard of care.

Statistical analysis

The primary objectives of this phase I/II clinical trial are to establish a therapeutic dose of Maraviroc and test the 100 day incidence rate of any GVHD in pediatric patients undergoing allogeneic stem cell transplantation against a historical incidence rate.

Phase I will consist of the determination of a therapeutic dose. A dose escalation procedure outlined in the study design will be conducted until a dose which yields 2 of 3 patients with AUC > 100ng/ml and no drug related toxicities.

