Verification of eligibility will be performed and appropriate documentation of informed consent will be documented for all subjects enrolled into the study. The timeliness of Adverse Event and Serious Adverse Event reporting will be monitored to ensure regulatory compliance. All case report forms (CRF) for the first subject enrolled into the study will be monitored for completeness and quality by comparing data in the case report forms to data in the source documents. Thereafter, a minimum of 10% of enrolled subjects' CRFs will be monitored for completeness and quality by comparing data in the case report forms to data in the source documents.

Data Safety Monitoring Plan

A qualified physician not associated with this particular protocol will be chosen as medical monitor for this study. The medical monitor will meet with the PI or designee and review study data/progress a minimum of every 6 months; more often at the discretion of the PI and/or medical monitor.

The medical monitor is required to review all unanticipated problems involving risk to subjects or others, unanticipated serious adverse events and all subject deaths associated with the protocol and provide an unbiased written report of the review.

At a minimum, the medical monitor should comment on the outcomes of the event or problem, and in the case of unexpected serious adverse event or death, comment on the relationship to participation in the study. Based on the review of these events, the monitor should make a recommendation regarding study continuation. All decisions regarding study continuation, modification, or termination will be reported immediately or

annually, as appropriate, to the IRB, FDA, and other appropriate agencies. Reports for events determined by either the investigator or medical monitor to be possible or definitely related to study participation and reports of events resulting in death should be forwarded in compliance with current IRB policy and applicable federal regulations.

Adverse Event Reporting

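### The only stopping rule that counts dose-limiting toxicities ends with the AUC phase, so stage 2 has no numeric trigger for non-engraftment or severe non-liver toxicity

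*Combined protocol and SAP*

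**What the plan says.** Stopping Rules has three items.

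- Rule 1 concerns visceral GVHD above 50% in the first 20 subjects. It does not count DLTs.
- Rule 2 stops the study if three of six subjects have a DLT by day +30 "at the initial dose in the first phase (AUC analysis) of the study, the study will be stopped".
- Rule 3 applies in both stages but to the liver only: "The study will be halted for any grade 4 liver toxicity occurring within 30 days of study drug administration", when no other cause is clear.

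Study design limits the AUC phase to ages 2 to 12, with 12 dose verifications and replacement of incomplete profiles. Then: "The second part of the study, where full AUC analysis will not be conducted, will enroll the remaining patients between the ages 2-40 years".

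Two other limits act in the first phase. Dose escalation criteria requires "No more than 0 of 3 or 1/6 patients on the first dose level experience a dose limiting toxicity by day 30", which gates escalation and does not stop the study. Statistical analysis accepts a dose when it yields "2 of 3 patients with AUC > 100ng/ml and no drug related toxicities".

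In stage 2 the other controls are these.

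- Drug is held in a patient for "Grade 3 or higher toxicity (exclusive of liver toxicity, see section above), not attributable to underlying disease". After recovery it may restart, but "Maraviroc will be discontinued if the AE recurs after re-challenge".
- A DLT ends study drug for that patient (Early termination of study drug).
- Grade 3 and higher events are recorded, and possibly attributable ones go to the FDA and IRB (Adverse Event Reporting).
- An independent medical monitor reviews study data at least every 6 months. The monitor must also review unanticipated serious events and "all subject deaths associated with the protocol and provide an unbiased written report of the review", and recommend on continuation (Data Safety Monitoring Plan).

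**The concern.** The Abstract hypothesises less visceral GVHD with no effect on engraftment. Non-engraftment by day 30 is a protocol-defined DLT, and failure to engraft is on the list of data to be collected. Yet once the AUC phase ends, no number of such cases obliges anyone to pause. The same holds for non-liver grade 4-5 toxicity.

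Single cases are plausible after any allogeneic transplant, so an excess is easier to judge from a running total than from one patient at a time. The patient-level holds act on one patient and set no limit across patients.

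The adult transplant experience at 300 mg twice daily, described under Previous Work Done in this Area, is reassuring but narrow: 38 patients, one reduced-intensity regimen, peripheral blood grafts. This trial admits all conditioning regimens, and also marrow and cord blood, from age 2.

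**Working it through.** The plan gives no operating characteristics for rule 2 and no background DLT rate, so there is no figure of its own to reproduce. Every DLT rate below is an assumption; 33% means 1/3.

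**Size of stage 2.** 65 total (Study design) − 12 = 53. This is a maximum, because replacements enlarge the AUC phase.

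**Expected DLTs in 53 patients.** 53 × 1/6 = 8.8; 53 × 0.20 = 10.6; 53 × 0.25 = 13.2; 53 × 1/3 = 17.7. At 33% the excess is 53 × (1/3 − 1/6) = 8.8 over a 1/6 background, 7.1 over 20% and 4.4 over 25%.

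**What the first phase would let through at 33%.** Rule 2 is passed with probability P(X ≤ 2 | n = 6) = (64 + 192 + 240)/729 = 0.68. The acceptance condition in Statistical analysis, read as no DLT in three patients, is passed with probability (2/3)³ = 0.30.

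**Example boundaries.** At looks after 10, 20, …, 60 patients, take the smallest count for which the posterior probability that the DLT rate exceeds p0 is above 0.975, with prior Beta(3p0, 3(1 − p0)). Trigger probabilities come from an exact patient-by-patient recursion over 65 patients, with the boundary acting alone.

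| Tolerated p0 | Boundary at 10/20/30/40/50/60 | Trigger probability at true rate |
|---|---|---|
| 1/6 | 5, 8, 10, 13, 15, 17 | 5% at 1/6; 14% at 20%; 41% at 25%; 87% at 33% |
| 20% | 6, 9, 11, 14, 17, 19 | 5% at 20%; 22% at 25%; 71% at 33% |
| 25% | 6, 10, 13, 16, 20, 23 | 6% at 25%; 36% at 33%; 74% at 40% |

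**DLTs averted, 1/6 boundary, 1/6 background.** Averted = (mean treated without the boundary − mean treated with it) × (p − 1/6), treating a pause as a permanent stop. With no other rule acting, p = 1/3 gives (65 − 33.8) × 1/6 = 5.2. That ignores rules already in the plan, so the same recursion was run with rule 2 stopping at three of the first six, and then with rule 3 halting at the first unexplained grade 4 liver DLT (share h of all DLTs).

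| True rate | Rules in force | Mean treated without / with boundary | Averted |
|---|---|---|---|
| 33% | rule 2 | 46.1 / 29.1 | 2.8 |
| 33% | rules 2 and 3, h = 5% | 29.7 / 22.1 | 1.3 |
| 33% | rules 2 and 3, h = 10% | 20.9 / 17.4 | 0.6 |
| 33% | rules 2 and 3, h = 20% | 12.6 / 11.9 | 0.1 |
| 50% | rule 2 | 26.3 / 11.2 | 5.0 |
| 50% | rules 2 and 3, h = 5% | 15.5 / 9.6 | 2.0 |
| 50% | rules 2 and 3, h = 10% | 10.8 / 8.4 | 0.8 |

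**Frequency of existing review.** 65 patients in about 60 months, reviewed every 6 months: 65/60 × 6 = 6.5 patients per review.

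**The case against.** The strongest reply is that stage 2 is already overseen. A physician outside the protocol sees the data about every 6.5 patients, more often than looks every 10, and can recommend stopping. Graft failure is a secondary endpoint and possibly related events reach the FDA and IRB. The known serious risk, hepatotoxicity, has a one-event halt in both stages. This stands. A reader might infer that stage 2 has no safety monitoring, that deaths go unreviewed, or that an excess could surface only through a formal count. The documents support none of these; the gap is the lack of a pre-stated number.

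A second reply is that a boundary cannot be calibrated from the documents. The protocol itself says most patients have severe toxicities during transplant, and eligibility is broad. This stands in part. A 1/6 boundary would pause needlessly with probability 41% if the background is 25%, and moving it to 25% cuts detection at 33% from 87% to 36%. The centre has to supply the rate.

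Third, the DLT definition differs between sections. Dose escalation criteria counts non-engraftment whatever its cause; Early termination of study drug counts it only if the investigator judges it drug-related. Any count must say which applies.

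Finally, Figure 1 is not shown, so a rule that appears only there cannot be excluded. A reader might also infer that an escalated dose would enter stage 2 unchecked. It would not, because Statistical analysis requires no drug-related toxicities before a dose is accepted. The point concerns patients treated after acceptance.

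**Conclusion.** The gap is real and narrow. Rule 2 is the only stopping rule that counts DLTs. It stops applying after the initial dose in the AUC phase, which leaves up to 53 of 65 patients without a numeric trigger for non-engraftment or non-liver grade 4-5 toxicity.

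The benefit of adding one is modest. A reader might take the figures without existing rules, about 5 excess DLTs averted at 33% and about 17 at 50%, as its size. They do not hold, because rules 2 and 3 remain in force. With rule 2 acting, the figures are about 2.8 and 5. With rule 3 also acting they are about 1.3, 0.6 or 0.1 at 33% (liver share 5%, 10% or 20%), and 2 or fewer at 50%.

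These results assume independent outcomes, no escalation, a 1/6 background and a pause that becomes a stop. The liver shares are assumptions too. This is a cheap improvement, not a fault that undermines the trial.

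**What to change.** Extend rule 2 with one paragraph and a small table.

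- Count day +30 DLTs cumulatively over all patients treated at the established dose, in both stages.
- State that the count uses the definition under Dose escalation criteria, with non-engraftment from any cause, and not the drug-related version under Early termination of study drug.
- When a pre-stated boundary is crossed, pause enrolment until the existing medical monitor gives a written recommendation.
- Set the tolerated rate from the centre's own background rates of non-engraftment and severe toxicity, and report the boundary's operating characteristics. The boundaries tabulated above are examples.

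Rules 1 and 3, the patient-level holds and the monitor's reviews stay as they are.

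The data and the monitor are already in place. Looks every 10 patients add little to a review about every 6.5, and waiting for day +30 adds about one or two patients per look. The main cost is a needless pause: about 5 to 6% likely if the boundary matches the background, but 14% or 41% if a 1/6 boundary meets a background of 20% or 25%.

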3. Abnormal ALT (≥ 5 X ULN) on day -3. (This criterion is to be assessed at study enrollment, but it will be confirmed again prior to the first dose of maraviroc)
4. Individuals who are HIV positive will not be enrolled in the study.

Treatment Plan

Dose and schedule of Maraviroc administration-

Maraviroc administration will start on day -3 and will end on day +30 after stem cell transplant, making the total number of days of drug administration 34 days. Our goal is to have steady state Maraviroc concentrations before stem cell infusion (on day 0) and continuing during the period of engraftment. The day of planned stem cell infusion will be recorded as day zero. If the stem cell infusion is given over 2 days, the first of those 2 days will be considered as day zero. Maraviroc will be administered twice daily orally or via enteral tube. Maraviroc absorption is somewhat reduced with ingestion of a high-fat meal; however, it can be given with or without food.

Dosing of Maraviroc will be based on body surface area, which will be assessed prior to starting maraviroc. This is based on the current congenital HIV trial using Maraviroc. We hypothesize that the optimal dose and exposure (as measured by the area under the concentration-time curve; AUC) for GVHD prophylaxis will likely conform to the optimal dose for the congenital HIV population (Table1). However, we recognize that stem cell transplant patients are more highly catabolic and have significantly more

concomitant medications than HIV patients, so are aware that we may find important PK differences.

BSA (m ²)	Dose of Maraviroc to be administered orally
<0.22	40 mg bid
0.2-0.43	100 mg bid
0.44-0.72	200 mg bid
0.73-1.19	300 mg bid
1.20-1.30	300 mg bid
1.31-1.73	300 mg bid
>1.73	300 mg bid

Table 1. Dosing of Maraviroc based on BSA [32].

Drug interactions with maraviroc occur with strong CYP3A4 inducers and inhibitors so these may not be used during the period of administration of maraviroc.

Enzyme Inducers	Enzyme Inhibitors
Carbamazepine	Amiodarone
Phenobarbital	Clarithromycin/Erythromycin
Phenytoin	Azoles (Keto/ Itra/ Vori/Posaconazole)
Rifampin	Verapamil
Rifabutin	Diltiazem
St. John's Wart	Grapefruit Juice
	Antiretroviral medications

Table 2. List of concomitant medications (CYP3A4 inducers and inhibitors) not allowed at enrollment or during study treatment

Adverse effects of Maraviroc

For a complete list of adverse effects, please see page 18 of protocol [23].

Study design-

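### Stopping rule 2 keeps enrolment open while a third DLT is analysed, so more children aged 2-12 can start the dose under review; rule 3's pause covers only liver events

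*Combined protocol and SAP*

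**What the plan says.** Stopping Rules, item 2, sets the trigger: "If 3 out of 6 subjects experience DLT by day +30 as defined above at the initial dose in the first phase". At that point the study is to stop. The item then says "Enrollment will not be suspended while the analysis is being conducted". It does not say what the analysis consists of, who performs it or how long it may take.

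Stopping Rules, item 3, deals with the liver: "The study will be halted for any grade 4 liver toxicity occurring within 30 days of study drug administration", provided no other cause is clear. Here "Enrollment will be suspended while an analysis of the toxicity is being conducted", and reopening needs the agreement of the Medical Monitor, the IRB and the FDA.

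The DLT definition that item 2 points back to is under Dose escalation criteria. It has three parts:
- (a) "Non-engraftment by day 30. Engraftment is defined as the first of three consecutive measurements", based on the neutrophil count, with no attribution clause;
- (b) grade 4 liver abnormalities, unless clearly due to the transplant and not the drug;
- (c) other grade 4-5 toxicity, with the same exception.

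On the first part of the study, Study design says "The age of enrollment for these patients will be limited to 2-12 years old". Twelve dose verifications are planned, and patients with incomplete PK profiles are replaced. Under Dose and schedule of Maraviroc administration, treatment runs from day -3 to day +30, "making the total number of days of drug administration 34 days".

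**The concern.** Rule 2 is the early toxicity stop for the youngest patients in the trial. Once a third DLT is reported among six subjects, the dose is a candidate for abandonment, yet the rule expressly leaves enrolment open until the analysis is finished. Parts (b) and (c) of the DLT definition need a judgement of cause in patients who are already very ill from transplant, so the analysis may take time.

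A child enrolled in that interval would receive the same dose. Escalation is allowed only with no DLT in 3 patients or at most 1 in 6, so 3 in 6 rules out a move to the next level.

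The contrast with rule 3 is hard to justify. One unexplained grade 4 liver event closes enrolment, while three non-engraftments, or three non-liver grade 4-5 toxicities (which include deaths), do not. The plan gives no reason for the difference.

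**Working it through.** The plan states no operating characteristics for rule 2, so there is no figure to reproduce. The check has two parts: whether other text closes the gap, and how large the gap is.

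**Does other text pause accrual?**
- Rule 3 covers only grade 4 liver toxicity within 30 days without a clear other cause. If one of the three DLTs were such an event, enrolment would already be suspended. The gap is therefore mainly parts (a) and (c) of the DLT definition.
- Discontinuation of therapy and Early termination of study drug stop or hold maraviroc in the affected patient. Apart from repeating rule 3, they do not touch enrolment.
- The Data Safety Monitoring Plan has the medical monitor review deaths, unanticipated problems and unanticipated serious adverse events: "Based on the review of these events, the monitor should make a recommendation regarding study continuation". That is advice after review, not an automatic pause.
- Places remain to be filled. Rule 2 counts 6 subjects and the first part plans 12 verifications, leaving at least 12 - 6 = 6, plus replacements.

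**How many more children could start?**
- Planned accrual, all ages (Number of Subjects): 65 / 60 months = 1.083 a month. Per week: 65 / (5 × 365.25) × 7 = 0.249.
- The share aged 2-12 is not given; 25-100% is assumed. That gives 0.25 × 1.083 = 0.27 to 1.08 a month.
- The length of the analysis is not given; 2-8 weeks is assumed.
- Lowest: 0.25 × 0.249 × 2 = 0.12 children. Highest: 1.00 × 0.249 × 8 = 1.99 children.
- With Poisson accrual, P(at least one start) = 1 − exp(−mean). This is 1 − exp(−0.12) ≈ 12% at the low end and 1 − exp(−1.99) ≈ 86% at the high end.
- At the all-ages rate, a 14-day analysis gives 0.50 expected starts (39% chance of at least one) and a 30-day analysis gives 1.07 (66%).

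**What risk would they face?** The observed rate is 3/6 = 50%, with an exact (Clopper-Pearson) 95% interval of 11.8% to 88.2%. The true rate is poorly known.

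**How often would the trigger be reached?** P(X ≥ 3) for X ~ Binomial(6, p), that is 1 − Σ C(6,k) p^k (1−p)^(6−k) over k = 0, 1, 2. The last column multiplies this by 0.12 and by 1.99, giving the expected extra starts before it is known whether the trigger will occur.

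| True DLT rate p | P(3 or more in 6) | Expected extra starts |
|---|---|---|
| 10% | 1.6% | 0.002-0.03 |
| 20% | 9.9% | 0.01-0.20 |
| 30% | 25.6% | 0.03-0.51 |
| 50% | 65.6% | 0.08-1.31 |

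**The case against.** The strongest reply is that the analysis in rule 2 may be no more than the tally that establishes whether 3 of 6 has been reached. Rule 2 says the study stops at that point, so on this reading enrolment continues only while the answer is unknown. The reading is plausible, but the interval between a third reported DLT and its confirmation is still open, and that is the interval at issue. A further reading, that the sentence refers to the AUC analysis named just before it, is unlikely: rule 1 carries parallel wording and involves no AUC.

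Second, non-engraftment under part (a) needs no attribution, so a third DLT of that kind may be settled almost at once. This stands, and it shortens the interval for such cases. The longer delays belong mainly to disputed events under part (c), or to earlier events whose cause is still unresolved.

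Third, the exposure is small, and the 2-8 weeks is an assumption. At about one patient a month, earlier DLTs could be attributed as they occur, leaving only the last one pending. This also stands. It limits the size of the problem without removing it.

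Fourth, the medical monitor can review more often and can recommend a halt. That is a real safeguard, but a discretionary one. Figure 1, the study flow, is not reproduced in the available text, so any gating of cohorts shown there could not be checked.

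Finally, the choice is explicit, and maraviroc's boxed warning concerns the liver, which may explain why only rule 3 pauses. That explains the stricter liver rule. It does not explain keeping enrolment open after three other DLTs in six children.

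**Conclusion.** The concern holds. It is a weakness in a stated design choice, not an internal contradiction. As written, further children aged 2-12 can be started at the initial dose after a third DLT has been reported and before the analysis is complete. The exception is when one of the events falls under rule 3.

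Once the trigger is in play, about 0.1-2.0 more children would be expected to start. This rests on an assumed 2-8 week analysis, an assumed 25-100% share aged 2-12, and accrual at the planned average; the upper end takes both assumptions at their maximum. Averaged over the chance of reaching the trigger, the figures are much smaller when the dose is reasonably safe. The point deserves action because the risk falls on children, is avoidable, and can be removed by a mechanism the plan already uses one item later.

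**What to change.** Replace the second sentence of Stopping Rules, item 2, with:

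> Enrollment may continue while the first six subjects are followed to day +30, but enrollment and new maraviroc starts will be suspended as soon as a third DLT is reported, pending confirmation; if confirmed, the study will be stopped.

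It would help to name who confirms the event and who may lift the pause, as item 3 does.

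The cost is one sentence and, if the third event is later judged not to be a DLT, a short pause in accrual. On the same assumptions, about 0.1-2.0 children would be delayed or would be transplanted on standard prophylaxis without maraviroc. The trigger count is reached with probability 1.6% at a true DLT rate of 10% and 9.9% at 20%, so for a safe dose the pause would seldom be used. Routine follow-up of the first six subjects would not hold up enrolment.
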